6.4.2 Humoral immune responses by IgG ELISA

Antigen-specific antibody will be assessed in plasma by IgG ELISA. This endpoint will be measured at baseline (Visit 3, Day 0) and 14 days after the 2nd vaccination (Visit 6, Day 70).

For assessment of the immunogenicity of H56:IC31, by IgG ELISA, only plasma samples measured at Visit 3 (Day 0) and Visit 6 (Day 70) for participants in the immunogenicity cohort are included (See

sections 1 and 2.2). All other IgG ELISA plasma samples taken from participants in the trial are defined as exploratory immunology/immunological correlate samples and are not the scope of this SAP.

Summaries will include immune response at visit 3 (Day 0) and visit 6 (Day 70) as well as fold increase from Day 0 to Day 70. Antibody titer will be presented in a plot by treatment and time. The immunogenicity analysis set will be used for analysis of humoral immune responses by IgG ELISA.

All visit 3 and visit 6 anti-H56 IgG antibody measurements for all participants in the immunogenicity cohort will be listed.

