2.1.3.1 Other Secondary Endpoints

- Rate of TB disease relapse, defined as participants meeting the primary endpoint of TB disease recurrence, AND determined by whole genome sequencing (WGS) of the *Mtb* isolate to be the same strain of *Mtb* as in the participant's original isolate from the time of diagnosis
- Rate of TB disease reinfection, defined as participants meeting the primary endpoint of TB disease recurrence, AND determined by WGS of the *Mtb* isolate to be a different strain than in the participant's original isolate from the time of diagnosis
- Antigen-specific cell-mediated immune responses by whole blood intracellular cytokine staining (WB ICS) at baseline (V3= Day 0), and 14 days after the 2nd vaccination (V6= Day 70) in the immunogenicity cohort

- Humoral immune responses by IgG ELISA of plasma samples taken from the immunogenicity cohort at baseline (V3= Day 0) and 14 days after the 2nd vaccination (V6= Day 70)

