7.4 Immunogenicity and Immunology Analyses

Immunogenicity and immunology analysis will be summarized for all time points as collected and as available. The immunogenicity endpoint analysis will be based on participants in the immunogenicity analysis set (defined in Section 7.1). No imputation for missing data will be performed. Data will be transformed as appropriate prior to analysis.

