7.4.2 Antigen-specific IgG ELISA Assay Using Plasma

This is a secondary endpoint in the study, see Section 2.1.3.1 and Table 3-2, and is the secondary immunogenicity endpoint. This endpoint will be measured in the immunogenicity cohort (see Table 2-1) at V3= Day 0 and V6= Day 70. For remaining participants, it is an exploratory endpoint at V3= Day 0, V6= Day 70 or at suspicion of a diagnosis of recurrent TB at the time of evaluation of TB recurrence. Antigen-specific antibody will be assessed in plasma by enzyme linked immunosorbent assay (ELISA). Summaries will include immune response at all available pre- and post-vaccination immunology time points, and change from pre-vaccination to post-vaccination time points.

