4.1 Statistical Considerations

Baseline is defined as the last assessment with available data prior to the first vaccination. No statistical tests comparing treatment groups at baseline will be performed.

Categorical data will be summarised by treatment group, using number and percentages of participants. Continuous data will be presented using the number of participants (N), mean, standard deviation (SD), median, lower quartile, upper quartile, minimum and maximum. Both the absolute values and the change from baseline will be presented, if applicable. For calculation of percentages the denominator will be the number of participants in the analysis set, unless otherwise specified.

Descriptive statistics for all endpoints will be presented by treatment group and Visit (if applicable) using observed cases, i.e., no imputation of missing data will be performed. Missing data for time to event endpoints is handled using censoring.

All presentations will at least be by treatment group.

For summaries presented by visit, scheduled time will be used, and trial visits will be labeled as below:

Visit	Label
3	Visit 3 (Day 0) - Baseline
4	Visit 4 (Day 14)
5	Visit 5 (Day 56)
6	Visit 6 (Day 70)
7	Visit 7 (Day 238)
8	Visit 8 (Day 421)

The following labels will be used in tables, figures, and listings:

Treatment	Label
H56:IC31: 5 µg H56/500 nmol IC31	H56:IC31
Placebo	Placebo

All will be presented in UK English.

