6.6 Multiplicity adjustments

In this two-armed trial there is no multiplicity issue with more comparators.

The primary analysis of the primary endpoint is based on the mITT analysis set. Analysis of the primary endpoint using other analysis sets are considered sensitivity analysis and adjustment for multiplicity is not necessary. The exploratory endpoints are exploratory in nature and no adjustment for multiplicity will be done.

The secondary endpoints, rate of TB disease relapse and reinfection are subdivisions of the primary endpoint, and no adjustment for multiplicity will be done.

For other secondary endpoints, no formal statistical analysis will be performed.

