Antigen specific CD4⁺ T cells expressing any of the cytokines, IL-2, IFN- γ , TNF- α , or IL-17 after stimulation with H56
Trial: <Trial id>
Program: <program_name>.sas - output: <output_name>.rtf - executed: DDMMMYYYY

Table 14.2.5.2: H56 protein-specific CD4⁺ T-cells expressing any combination of IL-2, IFN- γ , TNF- α or IL-17 (%) – WB ICS – Immunogenicity cohort
 <Layout similar to table 14.2.5.1>

Table 14.2.5.3: H56 protein-specific CD4⁺ T-cells co-expressing IL-2, IFN- γ , and TNF- α (%) – WB ICS – Immunogenicity analysis set
 <Layout similar to table 14.2.5.1>

Table 14.2.5.4: H56 protein-specific CD4⁺ T-cells co-expressing IL-2, IFN- γ , and TNF- α (%) – WB ICS – Immunogenicity analysis set
 <Layout similar to table 14.2.5.1>

Table 14.2.5.5: H56 protein-specific CD4⁺ T-cells co-expressing IL-2 and TNF- α (%) – WB ICS – Immunogenicity analysis set
 <Layout similar to table 14.2.5.1>

Table 14.2.5.6: H56 protein-specific CD4⁺ T-cells co-expressing IL-2 and TNF- α (%) – WB ICS – Immunogenicity cohort
 <Layout similar to table 14.2.5.1>

Table 14.2.5.7: H56 protein-specific CD8⁺ T-cells expressing any combination of IL-2, IFN- γ , TNF- α or IL-17 (%) – WB ICS – Immunogenicity analysis set
 <Layout similar to table 14.2.5.1>

Sponsor: SSI & IAVI	Document type:	Status: Final	
Vaccine: H56:IC31	Table shells	Version: 2.0	
Trial: POR A-055		Date: 15 SEP 2023	

Table 14.2.5.8: H56 protein-specific CD8⁺ T-cells expressing any combination of IL-2, IFN- γ , TNF- α or IL-17 (%) – WB ICS – Immunogenicity cohort

<Layout similar to table 14.2.5.1>

Table 14.2.6.1: Humoral immune responses by IgG ELISA – Immunogenicity analysis set

	H56:IC31	Placebo
Immunogenicity analysis set, N	xx	xx
Anti-H56 IgG (EU/mL)		
Visit 3 (Day 0) - Baseline		
N	xx	xx
Mean (SD)	xx.x (xx.x)	xx.x (xx.x)
Median	xx.x	xx.x
q25 - q75	xx.x - xx.x	xx.x - xx.x
Min - Max	xx - xx	xx - xx
Visit 6 (Day 70)		
N	xx	xx
Mean (SD)	xx.x (xx.x)	xx.x (xx.x)
Median	xx.x	xx.x
q25 - q75	xx.x - xx.x	xx.x - xx.x
Min - Max	xx - xx	xx - xx
Fold increase from Baseline to Visit 6 (Day 70)		
N	xx	xx
Mean (SD)	xx.x (xx.x)	xx.x (xx.x)
Median	xx.x	xx.x
q25 - q75	xx.x - xx.x	xx.x - xx.x
Min - Max	xx - xx	xx - xx

Page 1 of x

N: Number of participants, SD: standard deviation, q25: Lower quartile, q75: Upper quartile
 Trial: <Trial id>
 Program: <program_name>.sas - output: <output_name>.rtf - executed: DDMMMYYYY

Table 14.2.6.2: Humoral immune responses by IgG ELISA – Immunogenicity cohort

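### IgG ELISA: report geometric means and geometric mean fold rises with 95% CIs in place of an arithmetic mean of the fold increase

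*SAP*

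**What the plan says.** Protocol 2.1.3.1 makes IgG ELISA in the immunogenicity cohort, at Day 0 and Day 70, a secondary endpoint. Protocol 7.4.2 commits to description: "Summaries will include immune response at all available pre- and post-vaccination immunology time points, and change from pre-vaccination to post-vaccination time points". Protocol 7.4 adds, for all the immunology data, "Data will be transformed as appropriate prior to analysis".

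SAP 6.4.2 plans summaries of "immune response at visit 3 (Day 0) and visit 6 (Day 70) as well as fold increase from Day 0 to Day 70", with a plot by treatment and time and a listing. It names no scale, summary statistic, interval or arm contrast. The statistics come from the general rule in SAP 4.1: "Continuous data will be presented using the number of participants (N), mean, standard deviation (SD), median, lower quartile, upper quartile, minimum and maximum". Table shell 14.2.6.1 follows that rule, with rows for N, mean (SD), median, quartiles and range for anti-H56 IgG in EU/mL at each visit and for the fold increase, the two arms side by side. Its footnote reads "N: Number of participants, SD: standard deviation, q25: Lower quartile, q75: Upper quartile", so the means and SDs are the ordinary ones. Shell 14.2.6.2 repeats the layout for the immunogenicity cohort.

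SAP 6.6 covers endpoints other than the primary, relapse, reinfection and exploratory ones: "For other secondary endpoints, no formal statistical analysis will be performed".

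**The concern.** A fold increase is a ratio, and the natural average of ratios is geometric. The arithmetic mean gives a doubling more weight than a halving, so noise alone pushes it above 1. A reader who takes the mean row as the size of the response will see a rise in an arm where there is none, and an exaggerated rise where there is one.

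No row, including the unbiased median, carries an interval, and nothing estimates the vaccine response relative to placebo. The cohort is randomised, with 50 planned per arm, so the data would support such an estimate. At stake is how well one secondary immunogenicity endpoint is described; no decision rule depends on it.

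**Working it through.** **Inputs.** The rows of shell 14.2.6.1 and the default in SAP 4.1; 50 participants per arm (Protocol Table 2-1). The documents state no sample size, power or precision for IgG, so there is no planned figure to reproduce. They also give no SD for the change in log concentration; the range 0.1 to 0.5 on the log10 scale is assumed.

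**Direction.** Let R be the Day 70/Day 0 ratio. If nothing changes, in the sense that the two readings are exchangeable, R and 1/R have the same distribution. Then E[R] = E[(R + 1/R)/2], which is at least 1 and strictly greater whenever readings vary. This does not need log-normality.

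**Size.** For a log-normal ratio centred on no change, E[R] = exp(s²/2), with s = ln(10) × log10 SD. At a log10 SD of 0.3, s = 2.303 × 0.3 = 0.691 and E[R] = exp(0.239) = 1.27. The share of samples with a mean above 1 comes from 40,000 simulated samples of 50. The last column is 3 × exp(s²/2).

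| Assumed log10 SD | s | Expected arithmetic mean fold, no change | Samples of 50 with mean above 1 | True geometric threefold rise appears as |
|---|---|---|---|---|
| 0.1 | 0.230 | 1.03 | 79% | 3.08 |
| 0.2 | 0.461 | 1.11 | 93% | 3.34 |
| 0.3 | 0.691 | 1.27 | 98% | 3.81 |
| 0.5 | 1.151 | 1.94 | 99.9% | 5.82 |

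In the same simulations the sample median averaged 1.00 to 1.02, and the geometric mean was centred on 1.00 throughout.

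**Between arms.** The ratio of the two arithmetic mean folds is distorted by the factor exp((s_V² − s_P²)/2), where V is vaccine and P placebo. With equal SDs the factor is 1, and the simulated ratio was centred on 1.00. With unequal SDs it is not: at an assumed log10 SD of 0.5 for vaccine and 0.3 for placebo, it is 1.94/1.27 = 1.53 although the geometric mean folds are identical.

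**Precision of the replacement.** With 50 per arm and no covariate adjustment, the 95% CI for one arm's geometric mean fold rise is the estimate multiplied and divided by exp(2.010 × s/√50). For the between-arm ratio of fold rises the factor is exp(1.984 × s × √(2/50)).

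| Assumed log10 SD | One arm, ×/÷ | Ratio of arms, ×/÷ |
|---|---|---|
| 0.1 | 1.07 | 1.10 |
| 0.2 | 1.14 | 1.20 |
| 0.3 | 1.22 | 1.32 |
| 0.5 | 1.39 | 1.58 |

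**The case against.** Much can be said for the plan as written. The mean is one row of several: median, quartiles and range are in the same shell, and the median is essentially free of the inflation. Placebo stands beside vaccine, so a noise-driven rise would be visible in both columns. Titres are also plotted, and every Day 0 and Day 70 value in the cohort is listed.

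The missing contrast is a disclosed choice under SAP 6.6. The humoral objective, unlike those for safety, relapse and reinfection, does not mention comparison with placebo, and Protocol 7.4.2 promises only summaries. The protocol's line on transformation leaves the decision open.

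All of this stands, and it limits the point. Three things remain. Side-by-side columns remove the inflation only if the log-scale SDs match, which nothing in the documents assures. The median has no interval. And SAP 6.6 does not explain the difference in treatment from whole-blood ICS, another secondary endpoint in the same cohort at the same visits: its shell (14.2.5.1) omits the mean, and SAP Appendix A gives it between-arm comparisons with an effect size and 95% CI.

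**Conclusion.** The point holds as a minor improvement to reporting. The shells include a summary, the arithmetic mean of the fold increase, that is biased upward in expectation, and they omit the geometric summaries and intervals that would describe the endpoint properly. The bias follows from the algebra under no change. Its size, roughly 3% to 94%, rests on an assumed log10 SD of 0.1 to 0.5 and on log-normality.

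Four stronger readings are tempting and are not supported:

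- That IgG is summarised by arithmetic means alone: the shell also gives the median and quartiles.
- That the vaccine would necessarily look more immunogenic than placebo: with equal log-scale SDs the inflation is the same in both arms.
- That the SAP contradicts the protocol: the transformation wording is permissive, and the absence of formal analysis is stated openly.
- That this is the trial's only humoral endpoint: Protocol 2.1.4.1 has an exploratory IgG endpoint as well, which SAP section 1 places out of scope.

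No primary efficacy conclusion is touched.

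**What to change.** In SAP 6.4.2 and shells 14.2.6.1 and 14.2.6.2:

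- State that IgG is analysed on the log scale.
- Report the geometric mean concentration at Day 0 and Day 70, and the geometric mean fold rise, per arm with 95% CI.
- Keep the median, quartiles and range; drop the arithmetic mean (SD) of the fold increase.
- Add the vaccine/placebo geometric mean ratio with 95% CI, for example from a linear model for log Day 70 concentration adjusted for log Day 0 and site. Label it a descriptive estimate without a hypothesis test, and cross-refer to SAP 6.6 so that the status of the endpoint is unchanged.

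The cost is two table shells and a few lines of SAP text. No new samples or data are needed.

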6.5 Analysis and presentation of exploratory efficacy endpoints

Three exploratory efficacy endpoints linked to the primary endpoint are defined as follows:

1. Rate of TB recurrence, defined as participants meeting the primary endpoint of TB recurrence or who started TB treatment without confirmation of *Mtb* by culture of sputum
2. Rate of TB recurrence, defined as participants meeting the primary endpoint of TB disease recurrence based on confirmation of *Mtb* by Xpert MTB/RIF Ultra or culture of sputum
3. Rate of TB recurrence, defined as participants meeting the primary endpoint of TB disease recurrence or diagnosed between 30 days after the 1st vaccination and 14 days after the 2nd vaccination, based on confirmation of *Mtb* by culture of sputum

The analysis set for the 1st and 2nd exploratory endpoint (1. and 2. above) will be the mITT set and these analyses will be repeated using the ITT analysis set. The 3rd exploratory endpoint (3. above) will be analysed using the mITT2 set. See section 3 for definition of analysis sets.

The following analyses will be performed for the three exploratory endpoints: Time to TB disease recurrence will be estimated using the KM method and presented by treatment in a cumulative plot (inverted KM estimates) with 95% confidence bands, median time to TB, and the p-value from a two-sided log-rank test.

The endpoints will additionally be analysed using a Cox proportional hazard regression model, including treatment and site as categorical effects. Treatment group inference will be evaluated using a two-sided likelihood ratio test. Vaccine efficacy (VE) will be calculated as 1 minus the hazard ratio for H56:IC31 versus placebo and presented together with both 80% and 95% profile confidence limits.

The incidence of TB disease recurrence per 100 person-years of follow-up and associated 95% confidence limits will be presented by treatment. The relative risk between H56:IC31 and placebo with 95% confidence limits will be presented as well.

The Cox proportional hazard analysis will be repeated including country instead of site as categorical effect.

Details will be listed by trial site and participant.

6.5.1 1st exploratory endpoint: Rate of TB disease recurrence (relapse or reinfection)

1st exploratory Endpoint, Rate of TB disease recurrence (relapse or reinfection), is defined as participants meeting the primary endpoint of TB disease recurrence or who started TB treatment without confirmation of *Mtb* by culture of sputum.

The number (and percentage) of participants meeting the 1st exploratory endpoint will be summarised by treatment group. The summary will include the number of participants who started new TB treatment without culture confirmation of TB recurrence.

6.5.2 2nd exploratory endpoint: Rate of TB disease recurrence (relapse or reinfection)

2nd exploratory endpoint, Rate of TB disease recurrence (relapse or reinfection), is defined as participants meeting the primary endpoint of TB disease recurrence based on confirmation of *Mtb* by Xpert *MTB*/RIF Ultra or culture of sputum.

The number (and percentage) of participants meeting the 2nd exploratory endpoint will be summarised by treatment group. The summary will include the number of participants positive by Xpert *MTB*/RIF Ultra only and by Xpert *MTB*/RIF Ultra and culture.

6.5.3 3rd exploratory endpoint: Rate of TB disease recurrence (relapse or reinfection)

3rd exploratory endpoint, Rate of TB disease recurrence (relapse or reinfection), is defined as participants meeting the primary endpoint of TB disease recurrence AND participants diagnosed between 30 days after the 1st vaccination and 14 days after the 2nd vaccination, based on confirmation of *Mtb* by culture of sputum. The endpoint is similar to the primary endpoint, except that TB disease recurrence diagnosed between 30 days after the 1st dose and 14 days after the 2nd dose (or Day 70) is included as well.

The analysis set for this endpoint will be the mITT2 set.

The number (and percentage) of participants meeting the 3rd exploratory endpoint will be summarised by treatment group.

6.6 Multiplicity adjustments

In this two-armed trial there is no multiplicity issue with more comparators.

The primary analysis of the primary endpoint is based on the mITT analysis set. Analysis of the primary endpoint using other analysis sets are considered sensitivity analysis and adjustment for multiplicity is not necessary. The exploratory endpoints are exploratory in nature and no adjustment for multiplicity will be done.

The secondary endpoints, rate of TB disease relapse and reinfection are subdivisions of the primary endpoint, and no adjustment for multiplicity will be done.

For other secondary endpoints, no formal statistical analysis will be performed.

6.7 Sub-group and Centre Effects

The primary endpoint will in addition to the primary analysis be analysed using a Cox proportional hazard model including different categorical variables deemed to be of immunologic or epidemiologic importance, have biological plausible relation to the risk of TB disease relapse or have been associated with risk of TB disease relapse in previous literature. Please see section 6.2.1. for details.

The trial is multi-centre trial, and adjustment for centre effects for the statistical analyses is planned.

7 Statistical Methodology for Safety Endpoints

Safety will be considered for participants included in the Safety Analysis Set and reported by actual received treatment. No imputation of missing data is planned for safety endpoints except for imputation of partial dates, see section 8.2.

7.1 Safety Endpoints

The secondary safety endpoints are the following:

- Solicited adverse events occurring the first 7 days after each vaccination and all adverse events occurring the first 14 days after each vaccination
- Serious adverse events including medically important events occurring from the 1st vaccination through the end of the trial

Additional safety assessments are:

- Adverse events of special interest (AESIs) in the entire post-vaccination trial period
- Vital signs
- Weight
- Symptom directed physical examination
- Safety laboratory parameters

7.2 Analysis and Presentation of Safety Endpoints

7.2.1 Adverse Events

AEs will be regarded as treatment emergent AEs (TEAEs) if they occur after the 1st vaccination.

The collection periods for AEs are shown in the below table:

Table 3: Collection of AEs

Type of Event	Collection Period
Unsolicited adverse events (non-serious)	First 14 days after each vaccination (spontaneous adverse events, if any) Diary review and interview at study visit 14 days after each vaccination.
Solicited adverse events	First 7 days after each vaccination (solicited adverse events recorded daily in diary card) Diary review and interview at study visit 14 days after each vaccination.
Adverse events of special interest	Entire post-vaccination study period (i.e., 421 days).
Serious adverse events including medically important adverse events	Entire post-vaccination study period (i.e., 421 days).

Solicited adverse events are defined as events occurring within 7 days after a vaccination and of the following types:

- the injection site reactions *redness, swelling, and tenderness/pain*
- the systemic adverse events *fever* (i.e., events with PT *pyrexia* also named temperature reactions), *arthralgia, myalgia, fatigue, headache, rash, chills, and nausea*.

Solicited injection site reactions will be considered related to the IMP regardless of the causality assessment by the investigator. Therefore, related events consist of both solicited events and investigator-defined related events. Related AEs are defined as adverse reactions (ARs).

Presentations of serious adverse events (SAEs) will include medically important AEs.

An overall summary table of treatment emergent AEs by treatment will be made. The overall summary table will include number of events, number of participants, and proportion of participants in the safety analysis set reporting TEAEs (including solicited AEs), solicited AEs, AESIs, Treatment emergent SAEs, Fatal SAEs, related AEs, related SAEs, suspected unexpected SARs (SUSAR), AEs leading to discontinuation of IMP, AEs leading to discontinuation of trial, TEAEs by severity, and TEAEs by outcome. The same will be repeated for AEs occurring within 14 days after vaccination, SAEs, AESIs, solicited AEs and solicited SAEs occurring within the 7 days after each vaccination, and unsolicited AEs and SAEs occurring within the first 14 days after each vaccination.

Treatment emergent AEs, AEs within 14 days after vaccination, solicited AEs and solicited SAEs occurring within the 7 days after each vaccination, and unsolicited AEs and SAEs occurring within the first 14 days after each vaccination will be summarised by SOC and PT. The summaries will include number of events, number of participants, and proportion of participants reporting these events and will be tabulated by treatment. Additional summaries by SOC and PT will present number of events, and number and proportion of participants with AEs within 14 days after vaccination by severity, by causality, by age group (18-35 years, 36 years ->), and by sex.

The number of participants with solicited injection site reactions will be presented in a plot by type of reaction and maximum severity. The number of participants with solicited systemic events will also be presented in a plot by PT and maximum severity.

AESIs will be defined as either an AE marked by the investigator as an AESI or if the AE is covered by the list of PTs specified in the protocol, see Appendix B. AESIs are meant to be collected throughout the post-vaccination trial period. AESIs will be summarised by SOC and PT, including number of events, number of participants, and proportion of participants reporting these events by treatment arm. Similar summaries will be made for SAEs including medically important events.

The following listings of AEs will be made:

- AEs
- Solicited injection site reactions within the first 7 days after each vaccination
- Solicited systemic reactions within the first 7 days after each vaccination
- Unsolicited AEs within the first 14 days after each vaccination
- ARs (including SARs and SUSARs)
- AESIs
- SAEs
- AEs leading to withdrawal from treatment or trial

- Fatal SAEs
- Injection site reactions and systemic events occurring more than 14 days after vaccination
- Other non-serious adverse events occurring more than 14 days after vaccination, i.e., events not included in any of the above listings

AEs occurring before first vaccination including AEs in screening failures and in randomised participants never exposed to trial drug will be presented in a separate listing, if applicable.

